### **Benefit/risk associated with tremelimumab:**

In the clinical development program of tremelimumab and that of the related anti-CTLA-4 mAb, ipilimumab, a pattern of efficacy has emerged that appears to be consistent across tumor types. Response rates are generally low (~10%); however, in those subjects who respond, the responses are generally durable, lasting several months even in subjects with aggressive tumors (e.g., refractory metastatic melanoma). In a large Phase 3 study of tremelimumab versus DTIC/temozolomide in subjects with advanced melanoma, the median OS was 12.6 months for tremelimumab versus 10.7 months for DTIC/temozolomide (HR = 1.1416, p = 0.1272).

The safety profile across the tremelimumab nonclinical and clinical programs is dominated by immune-mediated reactions that can result in an inflammatory response. The important potential risks for tremelimumab that require further evaluation in clinical studies are immune-mediated gastrointestinal events such as colitis, endocrinopathies, dermatitis, pancreatitis, hepatitis, pneumonitis, neurotoxicities, cytopenias, and nonimmune-mediated infusion-related reactions, anaphylaxis and serious allergic reactions. Adverse events similar to those reported with ipilimumab were observed during clinical development of tremelimumab in melanoma, with diarrhea (40%), pruritus (23%), rash (22%), nausea (22%), and fatigue (17%) being the most common (Kirkwood et al, 2010). Grade 3 or higher AEs

observed were diarrhea (11%), fatigue (2%), rash (1%), nausea (1%), vomiting (1%), and anorexia (1%).

Potential risks associated with tremelimumab include immune-mediated gastrointestinal events including colitis, intestinal perforation, abdominal pain, dehydration, nausea and vomiting, and decreased appetite (anorexia); immune-mediated dermatitis including urticaria, skin exfoliation, and dry skin; immune-mediated endocrinopathies including hypophysitis, adrenal insufficiency, and hyper- and hypothyroidism; immune-mediated hepatitis including autoimmune hepatitis, and increased serum alanine aminotransferase and aspartate aminotransferase; immune-mediated pancreatitis including autoimmune pancreatitis, and lipase and amylase elevation; immune-mediated respiratory tract events including pneumonitis and interstitial lung disease; immune-mediated nervous system events including encephalitis, peripheral motor and sensory neuropathies, Guillain-Barre and myasthenia gravis (the latter reported with combination of tremelimumab and MEDI4736); immune-mediated cytopenias including thrombocytopenia, anemia and neutropenia; infusion-related reactions, anaphylaxis, and serious allergic reactions; and headache, fatigue, and pyrexia.

### **Benefits/risks associated with combination treatment:**

A total of 18 subjects have been treated, with 3 subjects each receiving 1 mg/kg tremelimumab and 3 mg/kg MEDI4736 Q4W, 1 mg/kg tremelimumab and 10 mg/kg MEDI4736 Q4W, 1 mg/kg tremelimumab and 15 mg/kg MEDI4736 Q4W, 3 mg/kg tremelimumab and 10 mg/kg MEDI4736 Q4W, 3 mg/kg tremelimumab and 15 mg/kg MEDI4736 Q4W, and 10 mg/kg tremelimumab and 15 mg/kg MEDI4736 Q4W. Overall, subjects have received between 0 and 7 doses of investigational products.

Across all dose cohorts, 17 of 18 subjects (94.4%) reported at least 1 AE (regardless of causality). The most frequently reported (> 3 subjects) AEs (all grades) were fatigue, pruritus, increased amylase, and arthralgia. Treatment-related AEs were reported in 13 of 18 subjects (72.2%). Of the 13 subjects, 4 had Grade 1, 3 had Grade 2, and 6 had  $\geq$  Grade 3 events as maximum severity. Treatment-related Grade 3 events that occurred in 2 or more subjects were fatigue (6 subjects), increased amylase (4 subjects); diarrhea, nausea, and increased alanine aminotransferase (3 subjects each); and abdominal pain, colitis, epigastric discomfort, vomiting, increased aspartate aminotransferase, decreased appetite, and arthralgia (2 subjects each). No consistent pattern in the nature, dose-relationship, frequency, or severity of AEs has been noted with escalating doses of the combination.

Nine subjects have reported 15 SAEs (Table 5.3.1.6-2). None of the preferred terms were reported in more than 1 subject. The majority of the SAEs were Grade 3 or higher in severity. Half of the SAEs were considered related to investigational products. Three subjects with SAEs of disease progression, colitis, and malignant neoplasm progression, respectively, permanently discontinued investigational products due to these events. The event of malignant neoplasm progression, considered not related to investigational products, resulted in death. In

addition, 1 subject died due to the SAE of polymyositis that was considered related to both MEDI4736 and tremelimumab.

### **Benefits/risks associated with the study procedures**

Both MEDI4736 and tremelimumab are administered intravenously. Possible risks associated with IV administration of the study drug(s) are infection, redness, swelling, and pain at the administration site.

## **2. STUDY OBJECTIVES**

The objective of this study is to determine whether MEDI4736 or combination therapy with MEDI4736 + tremelimumab are associated with favorable alterations of the intratumoral immunologic environment in subjects undergoing resectional surgery for MPM.

### **2.1 Primary objective(s)**

The primary objective of this study will be comparison of the ratio of intratumoral cytotoxic T cells to regulatory T cells (CD8/Treg) before and after treatment with combination MEDI-4736 and Tremelimumab checkpoint inhibitor therapy.

### **2.2 Secondary objective(s)**

The secondary objectives of this study are:

- 1) Comparison of the percentage of inducible T-cell co-stimulator (ICOS) positive intratumoral CD4 T cells before and after treatment with combination MEDI-4736 and Tremelimumab checkpoint inhibitor therapy.
- 2) Comparison of tumor tissue expression (Ventana assay) of programmed death-ligand 1 (PD-L1) before and after treatment with combination MEDI-4736 and Tremelimumab checkpoint inhibitor therapy.
- 3) Comparison of the ratio of the intratumoral CD8/Treg ratio in patients treated with combination therapy (MEDI-4736 and Tremelimumab) compared to either patients treated with MEDI-4736 alone, and separately compare to untreated patients.
- 4) Comparison of the percentage of inducible T-cell co-stimulator (ICOS) positive intratumoral CD4 T cells in patients treated with combination therapy (MEDI-4736 and Tremelimumab) compared to either patients treated with MEDI-4736 alone, and separately compare to untreated patients.

- 5) Comparison of tumor tissue expression (Ventana assay) of programmed death-ligand 1 (PD-L1) in patients treated with combination therapy (MEDI-4736 and Tremelimumab) compared to either patients treated with MEDI-4736 alone, and separately compare to untreated patients. These analysis will be post-protocol analysis based upon data obtained from the standard of care follow up in our post-surgical patients.
- 6) Comparison of overall survival in patients treated with either MEDI-4736 alone or MEDI-4736 plus Tremelimumab with historical untreated controls. These analysis will be post-protocol analysis based upon data obtained from the standard of care follow up in our post-surgical patients.
- 7) Comparison of recurrence-free survival in patients treated with either MEDI-4736 alone or MEDI-4736 plus Tremelimumab with historical untreated controls. These analysis will be post-protocol analysis based upon data obtained from the standard of care follow up in our post-surgical patients.

### **3. STUDY DESIGN**

#### **3.1 Overview of study design**

[figure not shown]
Subjects with MPM will undergo surgical mediastinal lymph node biopsy (cervical mediastinoscopy) and simultaneous surgical biopsy of the pleural tumor by thoracoscopy, at which time tumor tissue (at least 2 g) and peripheral blood will be collected for the study. These procedures are performed as our standard of care in the treatment of these subjects. The subject will be randomized. Three days to three weeks after the biopsy, 20 evaluable subjects (if tissue obtained) will be randomly treated with either MEDI-4736 alone (15 mg/kg once intravenously) (n=8) or MEDI-4736 (1500 mg once intravenously) plus tremelimumab (75 mg once intravenously) (n=8), or a control group (n=4) in a randomized controlled study design. There will be two treatment arms (MEDI4736 only and combination MEDI4736+tremelimumab) and one untreated arm (control). Randomization, stratified by receiving previous chemotherapy or not, will be performed and will help to minimize patient selection biases between three arms. Subjects under 30 kg will be treated with weight-based dosing for both MEDI4736 and Tremelimumab combination therapy. These patients are excluded from fixed based dosing to limit endotoxin exposure from the drug preparations. One to six weeks after the infusion, subjects will undergo resectional surgery, including extrapleural pneumonectomy (EPP) or pleurectomy/decortication (P/D), at which time the tumor will be removed (typically 200-1000 g) and obtained for study. Four patients that do not undergo treatment with MEDI-4736 or tremelimumab will be included as controls. Blood will be obtained after the induction of general anesthesia for both the thoracoscopy procedure and the EPP or P/D resectional procedure, as is routinely done in these procedures. The sixth rib will be obtained at the time of the resection.

After the removal of the tumor, our standard protocol includes intraoperative heated chemotherapy using a lavage of intracavitary cisplatin in the presence of conserved renal function (Sugarbaker et al., 2013, 2014; Richards et al., 2006).

Tumor tissues obtained either by thorascopic biopsy or by resectional surgery will be evaluated by time-of-flight mass spectrometry (CyTOF) to determine intratumoral CD8/Treg ratios and percentage of ICOS positive CD4 T cells, and by immunohistochemistry (Ventana assay) to determine the tissue expression of PD-L1. These variables will be compared before and after treatment (changes within the same patient tumor), or between treatment groups (MEDI-4736 alone, MEDI-4736+tremelimumab, untreated) following treatment. Additional hypothesis-generating analyses will include a comprehensive systems based evaluation of the intratumoral immune cell population composition and phenotype phenotype [e.g., dendritic cells, macrophages, myeloid derived suppressor cells (MDSC), neutrophils, T-cell subsets, natural killer (NK) cells, and B cells], and immune-related gene expression using the nanostring system within the tumors, blood, and bone marrow of patients in all treatment groups.

### 3.2 Study schema

**Figure 1** Study flow chart

## **Study Oversight for Safety Evaluation**

There are no stopping criteria for this study except for the following:

- a. Investigators decide to stop recruitment;
- b. Sponsor decides to discontinue the study;
- c. Subject withdraws consent at any time, for any reason.

Treatment may be put on hold, and pending full review of the data, the study may be stopped if any of the following criteria are met, and no further dosing or dose decisions will be taken pending a full safety review:

- a. 1 study drug-related serious adverse event is reported
- b. At least 4 subjects experience a similar unanticipated adverse event that is assessed

### **4. AS EITHER MODERATE OR SEVERE IN INTENSITY AND IS POTENTIALLY RELATED TO THE STUDY DRUG. SUBJECT SELECTION**

Potential subjects will be evaluated from our clinical population of patients with MPM who are eligible for surgical resection and meet all inclusion/exclusion criteria. Study investigators will determine eligibility from clinical chemistry, hematology, physical examination, and a review of medical history during screening prior to enrollment in the study.

#### **4.1 Inclusion criteria**

For inclusion in the study subjects must fulfill all of the following criteria:

1. Written informed consent and any locally-required authorization (e.g., HIPAA in the USA, EU Data Privacy Directive in the EU) obtained from the subject prior to performing any protocol-related procedures, including screening evaluations
2. Age  $\geq$  18 years at time of study entry
3. Eastern Cooperative Oncology Group (ECOG) performance status of 0 or 1
4. Adequate normal organ and marrow function as defined below:
  - Hemoglobin  $\geq$  9.0 g/dL
  - Absolute neutrophil count (ANC)  $\geq$  1.5  $\times$  10^9/L ( $\geq$  1500 per mm^3)
  - Platelet count  $\geq$  100  $\times$  10^9/L ( $\geq$  100,000 per mm^3)

- Serum bilirubin  $\leq$  1.5 x institutional upper limit of normal (ULN).
- AST (SGOT)/ALT (SGPT)  $\leq$  2.5 x institutional upper limit of normal unless liver metastases are present, in which case it must be  $\leq$  5x ULN
- Serum creatinine CL  $> 50$  mL/min by the Cockcroft-Gault formula (Cockcroft and Gault 1976) or by 24-hour urine collection for determination of creatinine clearance:

Males:

$$\text{Creatinine CL} = \frac{\text{Weight (kg)} \times (140 - \text{Age})}{72 \times \text{serum creatinine (mg/dL)}}$$

Females:

$$\text{Creatinine CL} = \frac{\text{Weight (kg)} \times (140 - \text{Age})}{72 \times \text{serum creatinine (mg/dL)}} \times 0.85$$

5. Female subjects must either be of non-reproductive potential (i.e., post-menopausal by history;  $\geq$ 60 years old and no menses for  $\geq$ 1 year without an alternative medical cause; OR history of hysterectomy, OR history of bilateral tubal ligation, OR history of bilateral oophorectomy) or must have a negative serum pregnancy test upon study entry.
6. Subject is willing and able to comply with the protocol for the duration of the study including undergoing treatment and scheduled visits and examinations including follow up.
7. Surgically resectable MPM with no disease extension beyond the ipsilateral hemithorax
8. Planned resectional surgery for MPM [extrapleural pneumonectomy (EPP) or pleurectomy and decortication (P/D)]
9. Any MPM histology (epithelial, mixed, sarcomatoid)
  - a. N0 or N1 nodal disease as present on preoperative chest CT and/or PET-CT
  - b. N2 nodule disease if no progression after 2 cycles of standard chemotherapy. Progression will be considered if additional N1 or N2 disease develop during chemotherapy.

## 4.2 Exclusion criteria

Subjects should not enter the study if any of the following exclusion criteria are fulfilled:

1. Involvement in the planning and/or conduct of the study (applies to both AstraZeneca staff and/or staff at the study site) Previous enrollment or randomization in the present study
2. Participation in another clinical study with an investigational product during the last 3 months
3. Any previous treatment with a PD1 or PD-L1 inhibitor, including MEDI4736
4. Receipt of the last dose of anti-cancer therapy (chemotherapy, immunotherapy, endocrine therapy, targeted therapy, biologic therapy, tumor embolization, monoclonal antibodies, other investigational agent) 30 days prior to the first dose of study drug 30 days prior to the first dose of study drug for subjects who have received prior TKIs [e.g., erlotinib, gefitinib and crizotinib] and within 6 weeks for nitrosourea or mitomycin C).
5. Current or prior use of immunosuppressive medication within 28 days before the first dose of MEDI4736, with the exceptions of intranasal and inhaled corticosteroids or systemic corticosteroids at physiological doses, which are not to exceed 10 mg/day of prednisone, or an equivalent corticosteroid
6. Any unresolved toxicity (>CTCAE grade 2) from previous anti-cancer therapy.
7. Any prior Grade  $\geq 3$  immune-related adverse event (irAE) while receiving any previous immunotherapy agent, or any unresolved irAE >Grade 1
8. Active or prior documented autoimmune disease within the past 2 years  
NOTE: Subjects with vitiligo, Grave's disease, or psoriasis not requiring systemic treatment (within the past 2 years) are not excluded.
9. Active or prior documented inflammatory bowel disease (e.g., Crohn's disease, ulcerative colitis)

10. History of primary immunodeficiency
11. History of allogeneic organ transplant
12. History of hypersensitivity to MEDI4736 or any excipient
13. History of hypersensitivity to tremelimumab or the combination of MEDI4736 + tremelimumab
14. Uncontrolled intercurrent illness including, but not limited to, ongoing or active infection, symptomatic congestive heart failure, uncontrolled hypertension, unstable angina pectoris, cardiac arrhythmia, active peptic ulcer disease or gastritis, active bleeding diatheses including any subject known to have evidence of acute or chronic hepatitis B, hepatitis C or human immunodeficiency virus (HIV), or psychiatric illness/social situations that would limit compliance with study requirements or compromise the ability of the subject to give written informed consent
15. Known history of previous clinical diagnosis of tuberculosis
16. History of leptomeningeal carcinomatosis
17. Receipt of live attenuated vaccination within 30 days prior to study entry or within 6 months of receiving MEDI4736 or MEDI + tremelimumab
18. Receipt of drugs with laxative properties and herbal or natural remedies for constipation within 90 days of receiving MEDI4736 or MEDI + tremelimumab
19. Receipt of sunitinib within 3 months of receiving tremelimumab
20. Female subjects who are pregnant, breast-feeding or male or female subjects of reproductive potential who are not employing an effective method of birth control
21. Any condition that, in the opinion of the investigator, would interfere with evaluation of study treatment or interpretation of patient safety or study results
22. Symptomatic or uncontrolled brain metastases requiring concurrent treatment, inclusive of but not limited to surgery, radiation and/or corticosteroids.
23. Subjects with uncontrolled seizures.

24. N3 nodal disease
25. History of interstitial lung disease/pneumonitis
26. No tissue is obtainable at thoracoscopy
27. Intraabdominal malignancy discovered at laparoscopy and proven pathologically, or nodal disease discovered at mediastinoscopy (N2 or N3 disease) and proven pathologically

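### Exclusion 3 requires patients to be naive to PD-1/PD-L1 inhibitors, but no criterion bars earlier anti-CTLA-4 therapy, the other half of the combination under test

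*Combined protocol and SAP*

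**What the plan says.** The primary objective (Section 2.1) compares intratumoral CD8/Treg "before and after treatment with combination MEDI-4736 and Tremelimumab checkpoint inhibitor therapy". Section 10.3 tests this with a paired t-test on the log ratio in the combination arm, planned at eight patients.

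Six items in Section 4.2, all repeated in the synopsis, bear on prior immunotherapy:

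- Exclusion 3 bars "Any previous treatment with a PD1 or PD-L1 inhibitor, including MEDI4736", with no time limit. It does not name CTLA-4 inhibitors.
- Exclusion 2 bars "Participation in another clinical study with an investigational product during the last 3 months".
- Exclusion 4 sets an interval for anti-cancer treatment, immunotherapy included: "monoclonal antibodies, other investigational agent) 30 days prior to the first dose of study drug".
- Exclusion 7 removes patients with a Grade 3 or higher immune-related event "while receiving any previous immunotherapy agent, or any unresolved irAE >Grade 1".
- Exclusion 13 concerns "History of hypersensitivity to tremelimumab or the combination of MEDI4736 + tremelimumab".
- Exclusion 21 is a discretionary clause: "Any condition that, in the opinion of the investigator, would interfere with evaluation of study treatment", or with the interpretation of safety or results.

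Section 3.1 puts the infusion three days to three weeks after the baseline biopsy, and resection one to six weeks after the infusion.

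**The concern.** The regimen has two halves. The eligibility rules demand that patients be new to one half and give no reason for treating the other differently. Exclusion 7 takes it for granted that some patients will have had immunotherapy, and exclusion 13 asks about hypersensitivity to tremelimumab, not about exposure to it.

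This bears on the primary endpoint because the protocol's rationale is that CTLA-4 blockade itself moves the measured quantities. The synopsis sample-size section cites a mouse melanoma model with a CD8/Treg ratio of 2 untreated and 11 after anti-CTLA-4. Section 1.4 says that anti-CTLA-4 treatment raised ICOS+ CD4 cells in patients, a secondary endpoint here, and mentions sustained increases. If a patient has already had such a drug, the biopsy taken as the baseline may already carry some of its effect. The primary test is made within one arm of eight pairs, so no comparison group absorbs a disturbed baseline, and a single patient has weight.

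**Working it through.** **1. Is there a bar elsewhere?** Taking the remaining items against prior ipilimumab or tremelimumab:

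- Exclusion 2 reaches back three months, and only for an investigational product in another study.
- Exclusion 4 reaches back 30 days from the first study dose.
- Exclusion 7 acts only on patients who had a severe or unresolved immune-related event.
- Exclusion 13 acts only on hypersensitivity.
- Exclusion 21 depends on the investigator's opinion and does not mention CTLA-4.

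None is an outright bar.

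**2. How close to the baseline biopsy can the earlier drug be?** Exclusion 4 counts back from the first dose, but the biopsy comes 3 to 21 days before that dose. For a patient just meeting the 30-day interval, the gap from last anti-CTLA-4 dose to biopsy is:

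- biopsy 21 days before infusion: 30 − 21 = 9 days
- biopsy 3 days before infusion: 30 − 3 = 27 days

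The post-treatment sample is taken 7 to 42 days after infusion. The 9-to-27-day range lies wholly inside that. Where exclusion 2 applies, the gap is longer, about three months.

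**3. Reproducing the planned power.** Inputs from the sample-size text in Section 10: log ratio 1.94 before and 2.87 after, SD 0.808, correlation 0.5, n = 8, alpha 5%.

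- SD of the difference = 0.808 × √(2 × (1 − 0.5)) = 0.808
- Planned change = 2.87 − 1.94 = 0.93
- Noncentrality = 0.93 / 0.808 × √8 = 3.26, with 7 degrees of freedom
- Two-sided paired-t power = 79.7%, which matches the stated 80%

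**4. Illustration of what pre-exposed patients could do.** The documents give no effect of prior anti-CTLA-4 on the later change, so the fraction of the planned change that such a patient still shows is an assumption. Mean change = 0.93 × ((8 − k) + k × f) / 8, for k pre-exposed patients who show fraction f. Power is from 200,000 simulated trials with the SD within patients at 0.808.

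| k of 8 | f | Mean log change | Fold change | Power |
|---|---|---|---|---|
| 0 | – | 0.930 | 2.53 | 80% |
| 1 | 1 | 0.930 | 2.53 | 80% |
| 1 | 0.5 | 0.872 | 2.39 | 73% |
| 1 | 0 | 0.814 | 2.26 | 63% |
| 2 | 0.5 | 0.814 | 2.26 | 66% |
| 2 | 0 | 0.698 | 2.01 | 45% |

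**5. Allowing for rarity.** If a share p of eligible patients were pre-exposed (assumed, not documented), the chance of at least one among eight is 1 − (1 − p)^8: 8% at p = 1%, 15% at 2%, 34% at 5%. Averaging power over the number of such patients gives 78%, 77% and 73% with no change (f = 0), and 79%, 79% and 77% with half the change (f = 0.5).

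**The case against.** The opening is narrower than exclusion 3 alone suggests. Section 11.2 describes tremelimumab as investigational, so earlier use would plausibly have come through a study and would face exclusion 2's three months. Exclusion 21 allows an investigator to turn such a patient away. The schedule of assessments records earlier mesothelioma treatment at screening, so exposure for that disease would at least be known. All of this stands, and it is why the point is a modest one. It does not close the gap: exclusion 21 is discretionary, and exclusion 2 does not cover a drug given outside a study.

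Exposure is also undocumented in this population. The mesothelioma experience with tremelimumab cited in Section 1.1 is in advanced, previously treated disease, whereas this trial takes resectable disease. That stands too; such patients are probably rare.

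A reader might go further and infer that prior exposure biases the paired change toward zero, or that power really is 63%. The documents do not support either. Section 1.4 says that the combination raises CD8/Treg more than monotherapy, and exclusion 3 keeps every patient naive to PD-1/PD-L1 blockade, so a patient who has had only anti-CTLA-4 could still respond to the combination. The same section says that in mice CTLA-4 blockade raises PD-1 expression on intratumoral T cells, so a larger response is conceivable. Nothing shows that a raised CD8/Treg persists in tumour after a washout.

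Lastly, the stated hypothesis does not mention CTLA-4 naivety, so the present wording is not an internal contradiction. That is right. The point is an unexplained asymmetry with a simple remedy.

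**Conclusion.** The point holds as a cheap improvement to eligibility. Patients must be naive to one half of the combination, prior exposure to the other half is restricted but not barred, and exclusion 4 alone lets the baseline be taken at an interval after anti-CTLA-4 that falls within the trial's own post-treatment sampling window. On the protocol's rationale, such a sample may not be an untreated baseline for CD8/Treg or ICOS+ CD4 cells.

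The size is uncertain. The planned 80% power is sound. With one pre-exposed patient among eight, power runs from about 80% (change unaffected) through 73% (half the planned change) to 63% (no change). The last is a worst case that sits badly with the protocol's own account of the combination. Once rarity is allowed for, the average loss at an assumed prevalence of 1% to 2% is about 1 to 3 points even in that worst case. How often such patients occur, and in which direction they would move the result, are assumptions.

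**What to change.** Reword exclusion 3, identically in the synopsis and Section 4.2, to cover any previous treatment with a PD-1, PD-L1 or CTLA-4 inhibitor, including MEDI4736 and tremelimumab. Exclusions 2, 4, 7, 13 and 21 can stay as they are and go on dealing with other prior therapy.

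The cost is a few words in an amendment and the loss of a rare patient with earlier anti-CTLA-4 treatment. Excluding such patients at entry keeps eight pairs and 79.7% power. Enrolling one and then leaving that patient out of the analysis would give seven pairs and 71.9%, so entry is the better place to settle it.
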